11.6 Ancillary Medications

All participants will have the option to receive ancillary medications. Dispensing of any medications will be recorded on a CRF. Dispensing of ancillary medications will be at the physician's discretion in accordance with clinical need to assist with the management of withdrawal signs and symptoms during detoxification but should be limited only to those medications listed below. Each type of ancillary medication will be placed into its own childproof bottle, appropriately labeled with the patient's name, date issued, contents and expiration date as well as dosing instructions for the patient. At the start of the detoxification, patients will be instructed on the use of each medication and told they can self-administer the medications in accordance with the instructions provided on the childproof bottle. Refills will be available to all participants during each scheduled clinic visit. Use of ancillary medications will be closely monitored for the duration of the study interventions. The following lists the dose, schedule, and indication for use of ancillary medications:

For anxiety and restlessness:

Days 1-7

lorazepam 1-2 mg q 6 hours prn; NTE 8 mg/24 hour **OR** oxazepam 15 - 30 mg po q6 hours prn; NTE 120 mg per 24 hours **OR** phenobarbital 15 - 30 mg. po q6 hours prn; NTE 120 mg per 24 hours **OR** hydroxyzine hydrochloride 50 mg, po q6 hours prn; NTE 200 mg per 24 hours

Day 8-13

lorazepam 1-2 mg q 6 hours prn; NTE 8 mg/24 hour **OR** oxazepam 15 - 30 mg. po q6 hours prn; NTE 60 mg per 24 hours **OR** phenobarbital 15 - 30 mg. po q6 hours prn; NTE 60 mg per 24 hours **OR** hydroxyzine hydrochloride 50 mg, po q6 hours prn; NTE 200 mg per 24 hours

For bone pain and arthralgias:

Days 1-13

Non-steroidal anti-inflammatory agent, such as ibuprofen (Advil, Motrin and others) 800 mg po q8 hours with food;

NTE 3200 mg in 24 hours **OR**

acetaminophen (Tylenol and others) 650 mg q 4 – 6 hours NTE 3900 mg in 24 hours **OR** methocarbamol (Robaxin and others) 500-1000 mg po q6 hours prn; NTE 2000 mg per 24 hours

For nausea:

Days 1-13

trimethobenzamide (Tigan) 250 mg po q8 hours prn; NTE 750 mg per 24 hours or 100/200 mg suppositories; NTE 400 mg per 24 hours

For diarrhea:

Days 1-13

loperamide (Immodium) 2 mg, 2 caps followed by 1 cap after each unformed stool: NTE 8 mg per 24 hours. **OR**

Donnatal 1-2 tablets po q 6-8 hours prn; NTE 8 tablets per day

For Insomnia:

Days 1-13

zolpidem tartrate (Ambien) 10 mg, 1 to 3 tabs, po qhs prn **OR** trazadone hydrochloride 50 mg, 1 to 3 tabs, po qhs prn **OR** doxepin hydrochloride 50 mg, 1 to 3 tabs, po qhs prn **OR** diphenhydramine 25 – 50 mg q 4-6 hrs prn; NTE 300 mg q 24 hrs

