10.0 INVESTIGATIONAL AGENTS

BUP/NX-combination:

Buprenorphine 2 mg and naloxone 0.5 mg or buprenorphine 8 mg and naloxone 2 mg sublingual tablets are manufactured by Reckitt and Colman Products (Hull, UK) and will be supplied through the National Institute on Drug Abuse and Research Triangle Institute.

Clonidine:

Clonidine (CATAPRES[®]- clonidine hydrochloride USP) is commercially available and is manufactured by Boehringer Ingelheim Pharmaceuticals, Inc., Ridgefield, CT. The clonidine to be used for this study is a 0.1 mg tablet for oral dosing and a transdermal therapeutic system (CATAPRES-TTS[®] - 1, 0.1 mg per day, for one week).

Ancillary Medications:

Ancillary medications used to treat opiate withdrawal side effects are commercially available and include:

Over the counter medications:

acetaminophen 650 mg

ibuprofen 200 mg loperimide 2 mg diphenhydramine 25 mg

Prescription medications:

oxazepam, tablets or capsules 15 mg and 30 mg
lorazepam, tablets 0.5 mg, 1 mg, and 2 mg
phenobarbital tablets, 15, 16 and 30 mg, capsules 16 mg
hydroxyzine hydrochloride tablets, 50 mg
methocarbamol tablets, 500 mg and 750 mg
trimethobenzamide capsules, 250 mg or 100/200 mg suppositories

Donnatal tablets or capsules – atropine sulfate 0.0194 mg, scoplamine hydrobromide
0.0065 mg, hyosyamine hydrobromide or sulfate 0.1037 mg, and phenobarbital 16
mg
zolpidem tartrate tablet, 5 and 10 mg
trazadone hydrochloride tablets 50 mg, 100 mg, 150 mg and 300 mg
doxepin hydrochloride tablets, 50 mg

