12.20 Ancillary Medication Tracking

The type of ancillary medication(s) dispensed will be recorded daily during detoxification on the Ancillary Medication Log Form.

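### Section 11.6 lets a patient take phenobarbital for anxiety and Donnatal for diarrhea together, up to 248 mg (days 1-7) or 188 mg (days 8-13) of phenobarbital a day within both stated limits

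*Protocol*

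**What the plan says.** Section 11.6 lists the permitted ancillary drugs by indication. One of the four options for anxiety and restlessness is phenobarbital:

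- Days 1-7: "phenobarbital 15 - 30 mg. po q6 hours prn; NTE 120 mg per 24 hours".
- Days 8-13: "phenobarbital 15 - 30 mg. po q6 hours prn; NTE 60 mg per 24 hours".

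For diarrhea on days 1-13 there are two options. One is loperamide, given as "2 caps followed by 1 cap after each unformed stool" with its own daily limit. The other is Donnatal: "Donnatal 1-2 tablets po q 6-8 hours prn; NTE 8 tablets per day".

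Donnatal's composition is given only in section 10.0, which lists "hyosyamine hydrobromide or sulfate 0.1037 mg, and phenobarbital 16", with the unit, mg, on the following line. So each tablet or capsule contains 16 mg of phenobarbital.

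On handling, section 11.6 says "Each type of ancillary medication will be placed into its own childproof bottle", and patients are "told they can self-administer the medications in accordance with the instructions provided on the childproof bottle". Section 12.20 describes the record kept: "The type of ancillary medication(s) dispensed will be recorded daily during detoxification".

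**The concern.** The word OR in section 11.6 separates choices within one indication. Anxiety and diarrhea are separate headings, and both are symptoms for which these withdrawal patients may be treated. One patient can therefore be given phenobarbital under the first heading and Donnatal under the second. The protocol neither excludes the pair nor says how Donnatal's phenobarbital is to be counted.

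What is at stake is dosing safety. The protocol sets a daily limit on a sedative, and for a patient on both drugs that limit no longer bounds how much of it is taken. From day 8 the phenobarbital limit is halved while the Donnatal allowance stays the same. Each bottle carries its own instructions, so a patient who follows both correctly has no reason to notice the overlap. Section 8.0 describes inpatient stays of typically 5 to 13 days, so some patients will be managing these bottles as outpatients for part of the period.

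**Working it through.** **Inputs**

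- Phenobarbital for anxiety: 15-30 mg every 6 hours; limit 120 mg (days 1-7) or 60 mg (days 8-13). Section 11.6.
- Donnatal for diarrhea: 1-2 tablets every 6-8 hours; limit 8 tablets a day (days 1-13). Section 11.6.
- Phenobarbital per Donnatal tablet: 16 mg. Section 10.0.

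**Reproducing the stated limits**

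- Phenobarbital, days 1-7: 30 mg x (24/6) = 120 mg, as stated.
- Donnatal: 2 tablets x (24/6) = 8 tablets, as stated.
- Phenobarbital, days 8-13: the schedule is unchanged, so 30 mg x (24/6) would still reach 120 mg. The 60 mg limit therefore genuinely restricts dosing, and equals 15 mg x (24/6).

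No stated figure is wrong.

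**Phenobarbital from Donnatal at its limit**

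8 tablets x 16 mg = 128 mg a day.

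**Both drugs together: mg from phenobarbital + mg from Donnatal**

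| Use of the two drugs | Days 1-7 | Days 8-13 |
|---|---|---|
| Both at their limits | 120 + 128 = 248 mg | 60 + 128 = 188 mg |
| Phenobarbital at its limit, Donnatal 2 tablets every 8 h (6 tablets, 96 mg) | 120 + 96 = 216 mg | 60 + 96 = 156 mg |
| Lowest dose and longest interval of each: 15 mg every 6 h (60 mg) plus 1 tablet every 8 h (3 tablets, 48 mg) | 60 + 48 = 108 mg | 60 + 48 = 108 mg |

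Against the limit on phenobarbital prescribed for anxiety, the top row is 248/120 = 2.07 times on days 1-7 and 188/60 = 3.13 times on days 8-13. The bottom row is 108/120 = 0.90 times and 108/60 = 1.80 times. These ratios only give scale, because the protocol does not present 120 or 60 mg as a ceiling on phenobarbital from all sources. Both drugs are taken as needed, so less frequent use gives less than the bottom row.

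**The case against.** The strongest reply is that nothing in section 11.6 is miscalculated or contradictory. Each limit belongs to one product for one indication and agrees with its own schedule. That stands: this is an interaction between two correct entries, not an arithmetic error.

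A second reply is that the list is a menu for the physician. Dispensing is left to the physician's judgement of clinical need, and section 11.6 says use will be watched closely. Patients are instructed on each drug, bottles are labeled with their contents, and dispensing goes on a CRF. Section 11.5.2 asks for daily monitoring of clonidine patients, and section 12.10 for daily adverse-event assessment with weekly physician review. A prescriber can find the 16 mg content in section 10.0 and avoid the pair. These safeguards are real and lower the likelihood of high combined dosing. None of them, however, flags the shared ingredient or adds it up. The log records the type of drug dispensed, and section 14.2.2 tallies dispensing by indication, so the two sources fall under different headings.

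Three stronger readings may tempt a reader, and the protocol does not support them:

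- *That 120 and 60 mg are all-source ceilings which Donnatal breaches.* Both figures are stated under the anxiety heading only. Donnatal alone may supply 128 mg a day, more than either figure, and breaks no stated rule.
- *That the combined doses are toxic.* The protocol gives no safe or toxic daily amount, so this cannot be judged from it.
- *That patients will take 248 or 188 mg, or that results are affected.* The totals need two as-needed drugs at full limit on the same day. The protocol gives no frequency of co-prescription, and nothing in it links the overlap to the primary endpoint or the sample size.

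**Conclusion.** The point holds as a gap in the ancillary-drug rules. A patient prescribed both drugs may take up to 248 mg of phenobarbital a day on days 1-7, or 188 mg on days 8-13, while obeying every limit the protocol states.

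The figures rest on three things: the 16 mg content given in section 10.0, a physician choosing both drugs for the same patient, and the patient using both up to their limits on one day. Severity is low to moderate. It is worth correcting because the remedy is nearly free and the safeguards already in place do not target the overlap.

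**What to change.** Add one sentence to section 11.6:

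> A patient receiving phenobarbital for anxiety is given loperamide, not Donnatal, for diarrhea; a patient receiving Donnatal is given a non-phenobarbital option for anxiety.

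Keeping the two drugs apart is preferable to a combined 120/60 mg limit. The protocol offers no basis for those figures as all-source ceilings, and such a limit on the pair would sit oddly beside the 128 mg a day that a patient on Donnatal alone may take. It also spares patients and staff from having to add doses across bottles.

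The cost is small. A patient on one of these drugs loses the other as an option, but loperamide remains for diarrhea, and lorazepam, oxazepam and hydroxyzine remain for anxiety. No new drug, visit, assessment, endpoint or change in sample size is needed.

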Patients will be excluded if they have any medical condition that would make participation medically hazardous, have clinically significant abnormalities in ECG, have known allergy or sensitivity to buprenorphine, naloxone, or clonidine, or have acute severe psychiatric condition, or immediate suicide risk. Patients who are dependent upon alcohol, benzodiazepines, or other depressants or stimulants, requiring immediate medical attention or who have participated in another investigational study within the last 30 days will be excluded. Patients receiving beta-blockers, calcium channel blockers, tricyclics, digitalis and other medication which may interact adversely with clonidine, and patients who have had methadone or LAAM maintenance or detoxification within 30 days of enrollment will also be excluded. Patients who have pending legal actions or for any reason are unable to remain in the area for the duration of the active phase of treatment will be excluded.

STUDY INTERVENTIONS: Patients randomized to the BUP/NX arm will receive daily doses for 13 days with sublingual administration of 2 mg buprenorphine -0.5 mg naloxone tablet(s) and/or an 8 mg buprenorphine – 2.0 mg naloxone tablet(s). The starting dose on day 1 is 4 mg/1 mg BUP/NX with an additional 4 mg/1 mg, if needed, escalating in a step-wise manner to 16 mg/4 mg BUP/NX on day 3 and tapering to 2 mg/ 0.5 mg BUP/NX by days 12 to 13. Patients randomized to the clonidine arm will receive oral clonidine (0.05 to 0.1 mg depending upon weight) every 4 to 6 hours for 24 hours not to exceed 0.6 mg total on day 1 and, assuming oral clonidine is well tolerated, a clonidine transdermal patch will be applied (0.1 mg/day/7-day patch with number of patches adjusted by weight). Oral clonidine will continue to be given on the second day of detoxification and increased to 0.2 mg every 6 hours or 0.1 mg every 3 hours not to exceed 0.8 mg over 24 hours. Patches will be worn for up to 13 days of detoxification. The dose of clonidine will be adjusted according to the proposed detoxification schedule, patient's weight, tolerance, and systolic blood pressure. Patients will receive counseling according to procedures in existence at each CTP throughout the study. Self-help detoxification handbooks will be distributed to all study participants.

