9.0 PATIENT SELECTION

A total of 360 male and female patients diagnosed with opiate dependence will be enrolled in the study (240 in the BUP/NX group and 120 in the clonidine group). Entry into this study is open to both men and women and to all racial and ethnic groups. Each of the participating CTP sites will enroll approximately 60 patients. Patients will be recruited by word of mouth, referrals from local narcotic treatment and outreach programs, outpatient and inpatient alcohol and drug abuse clinics, PCPs, local mental health centers and crisis clinics, public service announcements, newspaper advertisements and hospital emergency rooms. Recruitment advertisements will be approved by each site's Institutional Review Board (IRB).

9.1 Inclusion Criteria:

- 1. Treatment-seeking males and non-pregnant and non-lactating females, 15 years and older, who fulfill DSM-IV criteria for opiate dependence, report experiencing symptoms of opiate withdrawal, are currently physically dependent on opioids, and are need of medical assistance for opioid withdrawal.
- 2. Systolic blood pressure ≥ 100 mm Hg, and pulse ≥ 56 bpm.
- 3. Good general health or, in case of a medical/psychiatric condition needing ongoing treatment, under the care of a physician willing to continue patient's medical management and cooperate with the study physicians.
- 4. Agreeable to and capable of signing the informed consent approved by an institutional review board and, if under the age of 18 (excluding emancipated minors), assent and concurrent consent from a parent or legal guardian.
- 5. Use of one of the following acceptable methods of birth control by female patients of childbearing potential:
 - a. oral contraceptives
 - b. barrier (diaphragm or cervical cap) with spermicide or condom
 - c. intrauterine progesterone contraceptive system
 - d. levonorgestrel implant
 - e. medroxyprogesterone acetate contraceptive injection
 - f. complete abstinence from sexual intercourse

9.2 Exclusion criteria:

- 1. Medical condition that would make participation, in the opinion of the study physician, medically hazardous (e.g., acute hepatitis, unstable cardiovascular, liver or renal disease);
- 2. Clinically significant abnormalities in ECG.

- 3. Known allergy or sensitivity to buprenorphine, naloxone, or clonidine.
- 4. Receiving beta-blockers, calcium channel blockers, tricyclics, digitalis and other medications which may interact adversely with clonidine.

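### The ancillary list lets clonidine patients receive doxepin, a tricyclic, although patients on tricyclics are excluded at entry because of possible interaction with clonidine

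*Protocol*

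**What the plan says.** Section 9.2, item 4, excludes patients "Receiving beta-blockers, calcium channel blockers, tricyclics, digitalis and other medications which may interact adversely with clonidine". The synopsis gives the same list and the same reason: "tricyclics, digitalis and other medication which may interact adversely with clonidine". Section 11.4 randomises only after eligibility is confirmed, so the rule applies to everyone, whichever arm they later join.

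Section 10.0 names "doxepin hydrochloride tablets, 50 mg" among the ancillary prescription drugs. Section 11.6 gives the insomnia regimen for days 1–13, "doxepin hydrochloride 50 mg, 1 to 3 tabs, po qhs prn", as one of four alternatives. The others are zolpidem, trazodone and diphenhydramine. Access does not depend on arm: "All participants will have the option to receive ancillary medications". Dispensing is at the physician's discretion, but the list is closed: it "should be limited only to those medications listed below". Patients are "told they can self-administer the medications in accordance with the instructions provided on the childproof bottle".

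Clonidine runs over the same period. Oral dosing starts on day 1, and the synopsis says of the patches: "Patches will be worn for up to 13 days of detoxification". Section 11.5.2 has any remaining patches off by day 13.

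**The concern.** The protocol gives its own reason for excluding patients on tricyclics: the interaction with clonidine. Clonidine starts only after randomisation. The reason therefore bears on what is given together during the 13 days, and not only on what the patient was taking at the door. If doxepin belongs to the excluded class, the ancillary list permits the very combination that the entry rule guards against.

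What is at stake is patient safety in the clonidine arm and the coherence of the protocol that sites are asked to follow. A physician who reads a closed list with doxepin on it is told, in effect, that doxepin is acceptable for any participant.

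**Working it through.** No statistical figure is involved. The check sets the provisions side by side, with simple dose arithmetic.

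1. **Rule and reason.** Section 9.2(4) and the synopsis name tricyclics as a class and give interaction with clonidine as the reason. Neither states a mechanism, a dose or a severity.
2. **Drug class.** The protocol does not call doxepin a tricyclic. That it is one is standard drug classification, taken here as an assumption.
3. **Restriction by arm.** Sections 10.0, 11.5.2 and 11.6 contain no limit on doxepin for clonidine patients and no caution about the pairing.
4. **Dose permitted.** 1 × 50 mg = 50 mg, and 3 × 50 mg = 150 mg, per night.
5. **Overlap with clonidine.** Doxepin is allowed on days 1–13, and clonidine may be given from day 1 until day 13. That is at most 13 nights, or 12 if the last patch comes off before bedtime on day 13. Section 11.5.2 lets the clinician decide on day 7 whether to replace the patches or continue orally, so the overlap may be shorter.
6. **Patients to whom it is open.** 360 randomised 2:1 gives 360 × 1/3 = 120 clonidine patients (section 14.6). This is the number eligible for the drug, not a forecast of use.
7. **Route to the conflict.** A patient not on a tricyclic passes 9.2(4), is assigned to clonidine, and can be given doxepin for the first night with every step within protocol. The checklist in Appendix III asks whether prohibited medication was given, and a listed drug would not be flagged.
8. **Outcome touched.** Section 14.2.2 item 5 counts ancillary dispensing by indication, insomnia included. Its definition names no drug, so removing doxepin leaves it unchanged. The size of the menu within the indication falls from four options to 4 − 1 = 3.

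Two clonidine texts were read at the same time:

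- **Day-1 dose.** The synopsis gives a weight-dependent 0.05–0.1 mg as the repeated dose and mentions no test dose. Section 11.5.2 varies only the test dose by weight (0.05, 0.1 or 0.2 mg) and then schedules 0.1 mg every 4–6 hours. The 0.6 mg limit is the same in both.
- **Blood pressure.** Section 12.4 (for in-patients) and the Table 1 footnote allow from zero to several readings a day in the clonidine arm. Section 11.5.2 asks for daily monitoring, and its Day 1 text wants vital signs before each scheduled dose. Both of the looser texts refer the reader back to section 11.

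**The case against.** The best defence is that 9.2(4) is an entry criterion about drugs a patient is already receiving, and not a list of prohibited concomitant medication. That is correct. A reader might infer that dispensing doxepin would breach 9.2(4); the protocol does not support that. What conflicts is the stated reason for the rule, and that reason is not met by starting the tricyclic on day 1 instead of before entry.

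A second defence is that safeguards exist. Section 11.6 requires clinical need, physician judgement and close monitoring of ancillary use. Section 12.10 has adverse events assessed daily, with weekly physician review, and 11.5.2 lets patches be removed when clinically indicated. These reduce the risk, and they are why no harm can be asserted. They do not cure the conflict, because none of them tells staff that this pairing is a concern, while the list tells them that the drug is allowed.

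A third is that doxepin was listed deliberately, with strength and dose, in two places. That may be so, but nothing in the text reconciles it with the exclusion.

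On the side points, a reader might infer that light patients would be dosed differently under the two clonidine texts, or that in-patients on clonidine may go unmonitored. Neither follows. The synopsis gives no weight cut-off, so any comparison of daily totals would rest on an assumed one, and its own paragraph says that dosing is adjusted. Section 12.4 and the footnote defer to section 11, so 11.5.2 governs, and for outpatients a day without a reading is foreseen.

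**Conclusion.** The point holds as an inconsistency between the reason for an exclusion and the permitted ancillary list, and it should be fixed. The list allows 50–150 mg of doxepin nightly alongside clonidine, for at most 13 nights, with no restriction for the 120 planned clonidine patients.

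The conclusion rests on one assumption from outside the text, that doxepin is a tricyclic. It does not extend to a claim that patients will be harmed, or that any particular number will receive the combination: the drug is one of four as-needed choices, and the protocol gives no basis for a rate. Nor does it affect the trial's statistics: sample size, alpha, power and the primary endpoint stand as they are. The two clonidine wording points are editorial and lend no weight.

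**What to change.** Delete doxepin from sections 10.0 and 11.6 for both arms. This is the cleaner choice: the trial is open-label and ancillary dispensing by indication is one of the other primary outcomes, so an equal menu keeps the comparison even. Zolpidem, trazodone and diphenhydramine remain for insomnia.

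If the sponsor wants to keep doxepin for BUP/NX patients, mark it in both sections as not for patients assigned to clonidine, and accept slightly different lists between arms.

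The cost is one insomnia option, a short amendment and a notice to sites. No new data are needed.

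In the same amendment, as wording only:

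- Align the synopsis with 11.5.2: a test dose of 0.05–0.2 mg by weight, then 0.1 mg every 4–6 hours, with a day-1 maximum of 0.6 mg.
- In 12.4 and the Table 1 footnote, replace the zero-to-multiple frequency with a plain reference to section 11.5.2. Do not add a pre-dose check on every in-patient day: 11.5.2 states that check for Day 1, with the withholding rules carried to Day 2, and extending it would be a new requirement.
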